8.3 Assessment Procedures

1. Initial contact

Once we have made contact with the parent(s) we will introduce ourselves and explain the nature of the follow-up study and what will be involved. We will invite the parent(s) to ask any questions they might have. We will send the Participant Information Sheet to the family, if they have not already received it. If the parent(s) is interested in taking part, we will arrange a home visit.

2. Home visit

The researcher will visit the parent(s) at home (or in the clinic if they prefer). The researcher will discuss the study in more depth, make sure the parent has read and understood the Participant Information Sheet, and answer any questions the parent has. The parent will be asked to read and sign the consent form and the video-consent form. The researcher will then carry out the following interviews with the parent:

- Family information and demographics questionnaire.
- Social Communication Questionnaire (Lifetime and Current Forms)
- Repetitive Behaviour Questionnaire (Long Form)
- The Vineland Adaptive Behaviour Scales, 2nd Edition (VABS-II).
- The Child and Adolescent Service Use Schedule (CA-SUS).
- The Family History Interview Subject version (FHI-S)

If it is not possible to complete all the assessments within this visit, further home or clinic visits will be arranged with the family in order to ensure completion.

At the end of the home visit, the researcher will introduce the questionnaires and time diary to the parent and ask them to complete and return them to the researcher at the clinic visit.

The researcher will explain to the parent what will happen in the clinic visit. They will discuss which information sheet to leave for the child and provide a copy, asking the parent to go through it with the child prior to the visit. The researcher will also discuss with the parent how the child will be able to communicate assent.

3. Questionnaires

Between the home and clinic visit the parent will be asked to complete the following paper and online questionnaires:

- The Family Life Questionnaire
- Development and Well Being Assessment (DAWBA)
- Parent Wellbeing Questionnaire
- Parental Care Time Diary

If there are any difficulties with the parent filling these in independently, the researcher will sit with the parent and assist with issues of literacy or understanding the questions, whilst being certain not to influence the parent's responses. If the parent does not have access to the internet, the DAWBA will be conducted as an interview, in person or over the telephone, and the responses uploaded by the researcher.

4. Clinic visit (parent(s) and child)

The parent(s) and child will then attend the clinic setting. This will be a university assessment room or a clinic room in a hospital or health centre in their locality.

The researcher will go through the information sheet and assent form with the child and take written assent if applicable. Then the researcher will carry out the following assessments, which will be video-recorded for later coding and reliability purposes:

- Autism Diagnostic Observation Schedule (module 1, 2, or 3 depending on ability level of child)

- Clinical Evaluation of Language Fundamentals Fourth Edition UK (CELF-4 UK: core subtests of expressive and receptive Language)
- Receptive and Expressive One Word Picture Vocabulary Test (REOWPVT)
- BAS-III: the Non-verbal composite (4 subtests: Recall of designs, Pattern construction, Matrices, Quantitative reasoning) or the Early Years Non-verbal subscales
- Parent-Child interaction, coded at a later point by the researcher using The Dyadic Communication Measure for Autism (DCMA).

If it is not possible to complete all the assessments within this visit, further home or clinic visits will be arranged with the family in order to ensure completion. All appointments will be offered at a time convenient to the family, including early evenings, weekends and school holidays if necessary.

5. School visit

With consent from the parent, the researcher will contact the child's school and explain the study and invite the child's teacher to help us. If they agree, the researcher will visit the school and administer the following assessments.

- Vineland-II Teacher Rating Form
- MIPO Playground Observation

6. Post-assessment

Upon completion of the assessments, the family will be sent a report summarising the parent interviews and child assessments.

All travel expenses incurred by participants as a direct consequence of taking part in the study will be reimbursed. The main expense will be expenses to attend clinic appointments. This will constitute mileage and parking allowance, refund of public transport tickets, or the reimbursement of taxi journeys on occasion (if it is difficult for the family to attend by any other means). These expenses will be paid in accordance with local site procedures for payment of expenses to research volunteers.

All participating families will receive a £30 high street gift voucher in a thank you card at the end of their participation in the study. This is a token of appreciation for their time and efforts with the assessments and their continued involvement in the research programme. This amount reflects the amount of time families will need to dedicate to the study and is in line with other studies run by our team, which have found the amount to be appropriate.

9. MEASURES

9.1 Primary outcome measures

The primary outcomes measures are:

Autism Symptom Outcomes

- Autism Diagnostic Observation Schedule (ADOS) symptom severity

Language Outcomes - standardised scores of receptive and expressive language

- Clinical Evaluation of Language Fundamentals Fourth Edition UK
- Receptive/ Expressive One Word Picture Vocabulary Tests Fourth Edition

Family functioning and parental wellbeing

- -Family Life Questionnaire
- Parent Wellbeing Questionnaire

9.2 Secondary Outcomes measures

The secondary outcome measures are:

Adaptive Behaviour Outcomes

- -Vineland Adaptive Behaviour Scales, Second Edition
- -Vineland Adaptive Behaviour Scales, Teacher Rating Form, Second Edition
- Manchester Inventory for Playground Observation (MIPO)

Family Service Use and Burden of Care

- -Child and Adolescent Service Use Schedule (CASUS)
- -Parental Care Time Diary

Child Mental Health

-Development and Wellbeing Assessment (DAWBA)

9.3 Moderators/ Mediators

Developmental Quotient
-British Ability Scales-III

Broader Autism Phenotype
-Family History Interview

9.3 Description of Measures

9.3.1 Family and demographic information

The family information and demographics questionnaire is a bespoke questionnaire designed to obtain up-to-date information about contact details, family/ household composition, and parental employment and education. It is researcher-administered and takes about 10 minutes to complete. This information is used to make summary statements about the demographics of the sample and compare the two groups (from the original randomisation process) on key statistics.

9.3.2 Autism symptom outcomes

The following three assessments are outcome measures of autism symptom severity.

Social Communication Questionnaire (SCQ; Rutter, Bailey, Berument, Lord & Pickles, 2003)

This brief instrument is used to evaluate the communication skills and social functioning in children who may have autism spectrum disorders. It is available in two forms—Lifetime and Current—each composed of just 40 yes-or-no questions. Each form is completed by a parent or other primary caregiver in less than 10 minutes.

The questions cover the following content areas:

- Language use
- Non-verbal communication
- Social development
- Play
- Interests and behaviours

The *Lifetime Form* focuses on the child's entire developmental history, providing a Total Score that is interpreted in relation to specific cut-off points. The *Current Form* looks at the child's behaviour over the most recent 3-month period. It produces results that can be helpful in the measurement of change over time.

The SCQ content parallels that of the ADI-R, and the agreement between SCQ and ADI-R scores is high and substantially unaffected by age, gender, language level, and performance IQ. This indicates that the SCQ is a valid screener, providing a reasonable picture of symptom severity.

The Repetitive Behaviour Questionnaire (RBQ Long Form; Honey et al., 2012)

The RBQ is a 33-item questionnaire short-form of the repetitive behaviour interview [RBI] (Turner, 1995). Twenty-nine items examine specific repetitive behaviours and parents are required to rate these for severity or frequency on a 3 or 4 point likert scale dependent upon the behaviour. Behaviours examined include repetitive movements, sameness behaviour, repetitive use of language and circumscribed interests. Four additional items include a summary item which examines a child's overall variety of interests, and three qualitative items about the age repetitive behaviours emerged and the most problematic and noticeable behaviours. The RBQ has been used in 3 published studies of repetitive behaviour in children with ASD, OCD and language delay (Barrett et al., 2004, Zandt et al., 2007 and Zandt et al., 2009) aged between 4 and 16 years. The form can be completed in approximately 10-15 minutes.

Autism Diagnostic Observation Schedule-2 (ADOS2; Lord, Rutter, DiLavore, Risi, Gotham & Bishop, 2012)

This is a gold-standard direct observation measure of autism symptoms. It consists of a structured play-based assessment between researcher and child, videotaped for independent coding within domains of reciprocal social interaction, communication and repetitive and stereotyped behaviours. The ADOS includes four modules, each requiring 30-45 minutes to administer. One module is administered to each child, depending on his or her expressive language level and chronological age. The ADOS was used at Baseline and Endpoint assessment in the PACT study. In the follow-up we will be using newly-published severity and change additions.

9.3.3 Language and communication outcomes

The Clinical Evaluation of Language Fundamentals - Fourth Edition UK (CELF-4 UK; Semel et al., 2006) is a standardised assessment of receptive and expressive language abilities and difficulties. It assesses four aspects of language: morphology and syntax, semantics, pragmatics, and phonological awareness. This assessment will be administered to children with an estimated language level of five years or above. We will administer the core subtests of expressive and receptive Language and this will take 20-30 minutes to administer.

Receptive and Expressive One Word Picture Vocabulary Test, Fourth Edition (REOWPVT-4; Brownell et al., 2010). This is a brief pictorial standardised assessment of language comprehension and vocabulary. Children are asked to match a spoken word to an image or to name an object, action or concept from an image. It provides age-equivalents from two years into adulthood and takes 15-20 minutes to complete.

9.3.4 Non-verbal IQ

The British Ability Scales – Third Edition (BAS-III) is a standardised battery for assessing children's cognitive functioning. We will use the "non-verbal composite" which provides a standardised measure of non-verbal IQ. This consists of four subtests: Recall of designs, Pattern construction, Matrices, and Quantitative reasoning. For lower-functioning participants we will administer the Early Years Non-verbal subscales. These provide an age equivalence down to three years. The assessment will be administered by the researcher and takes around 30-45 minutes.

9.3.5 Family functioning, adaptation and mental health outcomes

The Vineland Adaptive Behaviour Scales, 2nd Edition (VABS-II; Sparrow et al., 2005) asks questions about the child's adaptive behaviour, that is, the personal and social skills needed for everyday living. The questionnaire is administered to the parent by the researcher using a semi-

structured interview format. There are five domains: communication, daily living skills, socialisation, motor skills and maladaptive behaviour. This takes about 20-60 minutes to complete.

The **Vineland Adaptive Behaviour Scales, 2nd Edition** (VABS-II; Sparrow et al., 2005) Teacher Rating Form assesses adaptive behaviour for pupils in school. This form uses a questionnaire format completed by the teacher or teaching assistant. The Teacher Rating Form contains the same Domains as the Survey Forms but covers content that a teacher would observe in a classroom setting. It takes around 20 minutes to complete.

The **Family Life Questionnaire** (Green et al., in prep) is a parental report across domains of parental confidence and self-efficacy, family functioning, child development and behaviour. This was developed for and used in the PACT Trial. It consists of statements about family life and parents tick boxes to indicate how often the statement applies to them. It takes 5-10 minutes to complete.

The Development and Well Being Questionnaire (DAWBA; Goodman et al., 2000) is a parental online rating of psychopathology and is used to identify important comorbidity (anxiety, ADHD, conduct and oppositional defiant disorder) in middle childhood. The parent will be asked to complete this online to provide information about comorbidity in the child. It takes about an hour to complete. If there are difficulties in completing this online, it will be administered as an interview over the phone, in the clinic or at home.

The **Parent Wellbeing Questionnaire** is a short tick-box questionnaire consisting of 26 items. It asked the parents about positive and negative aspects of their wellbeing. It comprises the General Health Questionnaire-12 and the Warwick and Edinburgh Mental Wellbeing Survey. Parents will be asked to complete this on a paper form. It takes about 5-10 minutes. This will provide a measure of parental health and wellbeing.

The Manchester Inventory for Playground Observation (MIPO) is a 10-minute observation of children's naturalistic play, interaction and behaviour within the school playground. A member of the research team not known to the child attends the school and observes the child and other children discretely during outdoor play-time. Behaviours of interest are noted with pen and paper and coded following the observation.

9.3.6 Parent child interaction

Parent and child are asked to play together for 15 minutes in a naturalistic way with a standardised set of materials. This interaction is video-recorded and coded at a later date using the **Dyadic Communication Measure for Autism** (DCMA; Aldred et al., 2011), an objective measure of parent-child dyadic communicative behaviours, which showed sensitivity to change and measured mediation in PACT.

9.3.7 Broader Autism Phenotype in parents

The **Family History Interview** - Subject version (FHI-S; Parr et al., in prep) is a reliable, semi-structured interview used to identify Broader Autism Phenotype behaviours and traits. These are milder ASD related traits sometimes seen in relatives of people with ASD. The FHI asks questions about social, communication and emotional strengths and difficulties in child and adulthood. The FHI-S also includes questions about depression, which will be a measure of mood history.

The primary PACT parent (who took part in the intervention, if in the intervention arm) will be interviewed one-to-one. This will be face-to-face or over the phone. The interview takes between 30 and 60 minutes.

9.3.8 Service use and Informal care

The **Child and Adolescent Service Use Schedule** (CA-SUS). Information will be collected from parents at interview using this schedule that was developed and tested in the PACT study. Given

the follow up period we will use a two-stage process successfully used previously, involving the application of the full CA-SUS to the 6-month period prior to interview and a brief version to collect key service data over the whole period since the PACT trial - including services relatively easy to recall over this period such as hospital and residential services and specific therapies for autism treatment. This interview will take place between researcher and parent and takes around 20 minutes.

Parents will also be asked to keep a **Time Diary** over two days (one week day and one weekend day). In this they will be asked to document the care they give to their child across the day and night. This is to measure the amount and type of care families provide for their child.

10. ANALYSIS

10.1 Sample size

Participants in the original PACT trial n = 152 were randomised to two groups: (1) Treatment as Usual, and (2) PACT Treatment plus Treatment as Usual. No further random allocation will take place. We aim to trace, contact and recruit at least 80% of the original sample (target n=>120).

10.2 Feasibility of follow-up rate

Previous follow-up studies in autism by the applicants have achieved equal or better retention rates; [name] ([name] et al., 2005) followed-up at age 7 years children who had previously been seen at 2 years and at 3 years of age as part of a preschool early intervention trial. Retention to age 7 years was 90% (26/29). [name] and [name] ([name] et al., in prep) followed-up at age 10 years children who had previously been seen at 2 years and at 5 years of age as part of a preschool early intervention study. Retention to age 10 years was 82% (36/44). In [name]'s child-adult study with mean length of follow-up = 37 years32 tracing rate was 91% (82/90) and agreement to participate rate was 67% (60/90).

This study will be adopted by MHRN/CLRN and we will have use of their staff to help with retracing and retention. The families are generally highly motivated to take part in research; since autism is a long-term disorder, families will continue to be concerned and preoccupied with their child's autism.

10.3 Power Calculation

The complexity of the specific context of the study means that the power calculations presented are illustrative. We assume a sample size of 120 (i.e. ignoring the additional power available from the PACT endpoint data for the 32 participants not followed up), two-tailed test and .05 significance criterion. Availability of repeated outcome measurement potentially increases our power. Estimates from PACT and the Early Diagnosis Study (Lord et al., 2006) suggest correlations of ADOS total scores of ~0.7 between baseline, PACT endpoint and follow-up to age 7 years. For estimating a mean difference using ANCOVA with a single pre- and two postrandomisation measures, we have a nominal power of 89% for ES=0.35SD, 96% for ES=0.40SD and 99% for ES=0.5SD (Stata sampsi). In a typical patient cohort we estimate that this last would correspond to a reduction of ~40% of AD and ASD cases being shifted below their corresponding diagnostic threshold and a 7-month improvement in Vineland Adaptive Behaviour Composite. For expressive language and Adaptive Behaviour correlations from baseline to endpoint and follow-up are rather smaller (~0.45) giving corresponding power estimates of 65% for ES=0.35SD, 76% for ES=0.4 and 92% for ES=0.5. For examining the independent effects of a set of prognostic factors for the sample as a whole we will have 78%, 89% and 95% power to detect the effects of a target covariate that explains respectively 3,4 and 5% of the variance in the presence of 4 confounders that explain a further 50% of the variance - plausible given the continuity from baseline measures (Stata, powerreg). For the testing of treatment moderating effects we estimated the power of a treatment group by covariate interaction on a change score (Gpower). Power of 80% requires a difference in standardized slope of 0.21, arguing for the very focused exploration of moderation proposed.

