5. STUDY OBJECTIVES

5.1 Primary Objectives

The PACT 7-11 study is designed to address three central questions:

1) Are the changes in developmental processes achieved in PACT sustained at 4-6 year follow up?

This question is a priority because it addresses an important issue of whether time-limited interventions of this kind are sufficient in a persistent developmental disorder, or whether longer or repeated phased interventions are necessary. The question will be answered through follow-up ascertainment of at least 80% of the original PACT Trial sample after 4-6 years in middle childhood, repeating comparable measures from the original trial, including:

- a. parental synchronous communication with the child (the targeted developmental process in the intervention)
- b. child communication initiations with parent
- c. measures of child communication and child and family adaptive functioning.
- 2) Does the enhancement of these early developmental variables result in later positive developmental outcomes in areas expected from theory?

Theory and independent longitudinal observation studies suggest that changing the early variables may impact on a number of specific longer-term outcomes including specifically child language and communication. The follow-up will also test generalised symptom and adaptation outcomes, which show modest effects at trial endpoint, as to whether the endpoint occurred before generalisation occurred. These hypotheses will be tested at follow-up by measuring:

- a. Child communication and language outcomes
- b. Autism symptoms
- c. Parent reported outcomes in child development, parental and family functioning
- d. Burden of parental care and service use
- 3) Can we use a treatment trial of this kind as a 'developmental experiment' to illuminate basic questions in the development science of autism?

The unique strength of this proposal is that the initial randomisation in the PACT trial allows for a causal interpretation of subsequent effects, something that does not apply in observational longitudinal studies. We will thus use the developmental follow-up of randomly allocated parallel cohorts and application of methodological innovations developed within the trial team to test a number of basic science hypotheses in autism:

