Appendix 1: Major post application revisions incorporated in this version

Appendix 2: Subsequent revisions occurring post data inspection

Document Revised for publication 29/1/16

STUDY DESIGN AND TRIAL ENDPOINT ANALYSIS

As described in Green et al. (2010).

FOLLOW-UP ANALYSIS

Overall strategy

Intention-to-Treat analysis of original trial/randomization design.

Primary outcomes: ADOS, DCMA, Language composite Secondary outcomes: VABS, RBQ, FLQ, DAWBA, SDQ, SCQ

Analysis goal: to use all the data to obtain good estimates of outcome where possible using growth curve approaches to yield a group difference at the median follow-up age (elaborated in PART A below) or as a simple follow-up difference or latent regression (elaborated in PART B below). No imputation of baseline data required.

Description

Follow-up rates to be described and balance in baseline covariates among those followed up to be described. CONSORT type diagram in on-line supplement.

Table 1 with Baseline and Follow-up mean/proportion/median and SD/range by treatment group for gender, age-at-recruitment, age-at-follow-up, numbers by centre.

Table 2 Follow-up mean/proportion/median and SD/range by treatment group for primary and secondary measures.

Treatment differences to be summarized in a tree-plot like effect size diagram.

PACT 7-11 Office, University of Manchester, [name]

PACT 7-11 Combined Protocol and Analysis Plans with Changes 1/2/16 Page 24

Part A

Growth Curve Analysis model: For **repeated measures** (i.e. those already measured in PACT) treatment group comparisons at the mean age at follow-up based on a piecewise growth curve model with separate correlated pieces over PACT and PACT7-11. Baseline variables for which groups are imbalanced will be included as fixed-effect covariates with interactions of group and time to allow different effects during PACT and PACT7-11. Group differences will be estimated at the median follow-up age.

Primary Outcomes

1. ADOS-2 overall Comparative Severity Score (CSS)². Then report Social Affect and Restricted and Repetitive Behavior Comparative Severity Scores³ descriptively. The numbers completing each ADOS Module will be reported.

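### Section 10.3 gives power for the effect averaged over the PACT endpoint and the follow-up, not for the follow-up difference that the analysis plan estimates

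*Combined protocol and SAP*

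**What the plan says.** Protocol section 10.3 takes 120 children, with a "two-tailed test and .05 significance criterion", and describes its calculations as illustrative and its power as nominal. For ADOS it assumes "correlations of ADOS total scores of ~0.7 between baseline, PACT endpoint and follow-up to age 7 years", and then states: "For estimating a mean difference using ANCOVA with a single pre- and two postrandomisation measures, we have a nominal power of 89% for ES=0.35SD", with 96% at 0.40 SD and 99% at 0.50 SD, naming Stata sampsi as the source. For expressive language and adaptive behaviour it takes a baseline correlation of about 0.45 and reports 65/76/92%. It gives no correlation between the two later measures for that second set.

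The analysis plan for the primary follow-up paper was agreed before the follow-up data were inspected by treatment group. For repeated measures (Part A) it fits a piecewise growth curve with group-by-time terms and says: "Group differences will be estimated at the median follow-up age". For the DCMA and the parent Vineland it adds that a single estimate will be built at that age. The language composite is in Part B, where the follow-up score alone is regressed on group, covariates and any similar baseline measure. Protocol section 5.1 asks as its first question: "Are the changes in developmental processes achieved in PACT sustained at 4-6 year follow up".

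Protocol section 10.4 says that the growth models will describe an effect over the whole course, and also whether early effects grow or fade.

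**The concern.** ANCOVA on two post-randomisation measures gains precision by averaging them. That gain belongs to the average effect. It does not carry over to the difference at the later occasion. When a model lets the group difference vary over time, and the data are complete, the earlier measure adds essentially nothing to the estimate at follow-up.

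A reader of section 10.3 would take 89% as the chance of detecting a 0.35 SD difference in ADOS at follow-up. These are the only power figures for a treatment effect in the documents. The study asks about persistence, so a non-significant follow-up result is open to being read as an effect that has gone. How safe that reading is depends on the power for that contrast.

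**Working it through.** **Inputs.** From section 10.3: "We assume a sample size of 120", two-sided 0.05, r=0.7 among all ADOS occasions, and r=0.45 from baseline for the second set. Assumed: 60 per arm (the split is not given), and a correlation of 0.70 to 0.75 between the endpoint and follow-up measures in the second set (also not given).

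**Formula.** With one baseline and k later measures, baseline correlation r and correlation ρ between later measures, the variance factor for the mean of the later measures is F = (1+(k−1)ρ)/k − r². Then SE = √(2F/60), and power = Φ(ES/SE − 1.96).

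**Step 1: reproduce the stated figures (k=2).**
- ADOS: F = (1+0.7)/2 − 0.49 = 0.36 and SE = √(0.72/60) = 0.1095. Power is 89.2/95.5/99.5%, against the stated 89/96/99%.
- Second set, ρ=0.75: F = 0.875 − 0.2025 = 0.6725, giving 64.7/76.2/91.6%. With ρ=0.70, F = 0.6475, giving 66.4/77.7/92.5%. Both are close to the stated 65/76/92%. With ρ=0.45 the result is 75.6/85.8/96.6%, which does not match, so the stated set implies ρ of about 0.70 to 0.75.
- A single later measure reproduces neither set.

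**Step 2: follow-up difference, baseline conditioned on (k=1, F = 1 − r²).**
- ADOS: F = 0.51 and SE = √(1.02/60) = 0.1304. At 0.35 SD, 0.35/0.1304 − 1.96 = 0.724, so power is 76.6%. At 0.40 and 0.50 SD it is 86.6% and 97.0%.
- r=0.45: F = 0.7975 and SE = √(1.595/60) = 0.1630. Power is 57.4/68.9/86.6%.

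**Step 3: let the 32 children not followed up contribute baseline and endpoint data by maximum likelihood** (76 per arm at those occasions, 60 at follow-up). The partial correlation of endpoint and follow-up given baseline is p = (ρ − r²)/(1 − r²), and F = (1 − r²)[(1 − p²) + p²·60/76].
- ADOS: p = 0.21/0.51 = 0.412 and F = 0.492, giving 78.0/87.8/97.4%.
- r=0.45: ρ=0.70 gives F = 0.732 and 61.0/72.6/89.3%. ρ=0.75 gives F = 0.718 and 61.9/73.4/89.8%. This can apply to the parent Vineland. It cannot apply to the language composite, which has no endpoint equivalent in the model.

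**Step 4: baseline group means left free.** The analysis plan models baseline ADOS as one of the outcomes, with a group main effect. If the contrast is then the raw difference at follow-up, F = 1 and SE = √(2/60) = 0.1826, giving 48.3/59.1/78.2%. With the 32 children, the share of follow-up variance explained by baseline and endpoint together is R² = 2(0.49)/1.7 = 0.576. Then F = 0.424 + 0.576·60/76 = 0.879, giving about 53/65/83% for ADOS.

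| Power (%) at 0.35/0.40/0.50 SD | ADOS, r=0.7 | r=0.45 |
|---|---|---|
| Stated (average of two occasions) | 89/96/99 | 65/76/92 |
| Follow-up, baseline conditioned on | 77/87/97 | 57/69/87 |
| Same, with the 32 by ML | 78/88/97 | 61–62/73/89–90 |
| Follow-up, baseline means free | 48/59/78 | 48/59/78 |

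For ADOS at 0.35 SD, the type II error goes from 11% to 23%. With baseline conditioned on, 89% power for ADOS needs an effect of about 0.42 SD.

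**The case against.** Section 10.3 does not hide its method. It says that two post-randomisation measures are used and warns that the figures are illustrative. Section 10.4 plans to describe an effect over the whole course, and the two-measure calculation suits that quantity. All this stands. The power section is not wrong in itself; it does not match the estimate chosen in the later analysis plan. The warning words signal approximation. They do not tell a reader that the power refers to an average that includes the already reported endpoint. The area-under-the-curve summary in Appendix 2, which is closer to an average, was added only after data inspection.

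Section 10.3 also says that it ignores power from the 32 children not followed up. That is fair, and for the parent Vineland it brings the shortfall down to about 2 to 4 points. For ADOS it recovers only about one point.

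The cohort is fixed at 152, so no sample size rests on these figures. At 0.50 SD, the only effect size that section 10.3 translates into clinical terms, ADOS power moves only from 99% to 97%.

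A reader might go further and infer an arithmetic error. The documents do not support that, because the stated figures reproduce. A reader might also take 77/87/97%, or 48/59/78%, as the power of the plan. Neither can be fixed from the text: the analysis plan does not say whether baseline group means are constrained, and r=0.7 was given for ADOS total scores, while the outcome is an ordinal severity score. Nor does the question on sustained effects in section 5.1 settle the matter for ADOS, since it lists parent–child interaction, communication and adaptive measures, and autism symptoms come under the second question.

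**Conclusion.** The concern holds as a mismatch between the powered quantity and the planned estimate. With baseline conditioned on, the stated power exceeds that for the follow-up difference by about 12, 9 and 2 points for ADOS, and by about 8, 7 and 5 points for outcomes with r=0.45. It matters most at 0.35 SD. The language composite is the clearest case, because no second post-randomisation measure enters its analysis.

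These sizes rest on 60 per arm, the correlations in section 10.3, ADOS treated as continuous, and a language baseline measure that correlates about 0.45 with the composite. Handling of baseline is the largest unknown, since leaving baseline means free by group would lower power much further. Section 10.3 gives no correlation for the DCMA child initiations outcome, so no figure can be derived for it. The point deserves correction but does not threaten the design or the planned analyses.

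**What to change.** In section 10.3, label 89/96/99% and 65/76/92% as power for the effect averaged over the PACT endpoint and the follow-up, and state the endpoint-to-follow-up correlation used for the second set. Add power for the follow-up difference with its assumptions: about 77/87/97% for ADOS (78/88/97% with the 32 children by ML) and about 57/69/87% for outcomes with r=0.45 (61–62/73/89–90% for the parent Vineland with the 32, if the endpoint-to-follow-up correlation is 0.70 to 0.75).

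In Part A of the analysis plan, say whether the growth models condition on baseline or hold baseline group means equal, and note that the added figures require one of these. If baseline means are left free and the raw follow-up difference is reported, give about 48/59/78% instead (53/65/83% for ADOS with the 32).

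The cost is a few lines of text and a less favourable stated power. No participants, visits or data are added.
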